1.4. Summary of the Known and Potential Risks and Benefits of Voxelotor

Clinical data to date have shown that treatment with voxelotor results in a dose-dependent increase in Hb within 2 weeks that is maintained through 24 weeks, and with an associated decrease in clinical measures of hemolysis which correlates with drug exposure (Brown, 2018; Vichinsky, 2018). In a global, multicenter, Phase 3, double-blind, randomized, placebo-controlled trial of voxelotor in participants with SCD (Study GBT440-031), the percentage of participants achieving an Hb response (> 1 g/dL Hb increase from Baseline at Week 24) was dose dependent: 51.1% for the voxelotor 1500 mg group, 32.6% for the voxelotor 900 mg group, and 6.5% for the placebo group ($p < 0.001$ for each voxelotor dose vs placebo). In the 1500 mg group, the mean Hb increase at Week 24 was 1.14 g/dL and in placebo -0.08 g/dL. Consistent with the improvement in Hb, the reductions in hemolysis measures (indirect bilirubin, absolute reticulocytes, percent reticulocytes, and LDH) were observed with both voxelotor 1500 mg and 900 mg compared to placebo. These were significant for indirect bilirubin (-25.9%, $p < 0.001$) and percent reticulocytes (-24.5%, $p < 0.001$) (Vichinsky, 2019).

Based on available data, voxelotor has been well tolerated in adult and adolescent patients with SCD. The most common adverse reactions in participants with SCD ≥ 12 years old in $\geq 10\%$ of participants treated with voxelotor 1500 mg with a difference of $> 3\%$ compared to placebo included headache, diarrhea, abdominal pain, nausea, fatigue, rash, and pyrexia. Other clinically relevant and less frequent adverse reactions included drug hypersensitivity ($< 1\%$). There were no reported events of anaphylaxis or anaphylactoid reactions in the clinical development program. The majority of treatment-emergent adverse events (TEAEs) were Grade 1 to Grade 2 in severity, clinically manageable, and reversed or resolved. Overall, the safety profile was similar in participants who were or were not receiving HU concomitantly, and between adults and adolescents. In SCD studies with voxelotor, the incidence of VOCs was similar to placebo

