1.5.1. Study Rationale

In the pivotal Phase 3 Study GBT440-031, voxelotor was shown to have a dose-dependent (1500 mg > 900 mg orally daily), and clinically meaningful increase in Hb, as well as concurrent reductions in clinical measures of hemolysis. Study GBT440-029, is designed to assess tolerability, safety, and PD of voxelotor dose levels higher than 1500 mg daily (the maximum dose in the pivotal Phase 3 study) and to compare these results to the 1500 mg dose. The rationale for this study is based on an exposure-response analysis from the pivotal Study GBT440-031, which showed a linear relationship between whole blood voxelotor and %Hb occupancy and efficacy as measured by improvement in Hb (see Figure 1 below) and hemolysis markers. The 1500 mg dose led to a mean Hb occupancy of 29% and led to a mean Hb increase of 1.1 g/dL. At 3000 mg of voxelotor, assuming a linear relationship, the mean Hb occupancy is projected to be 49.3% with a Hb increase of 2.04 g/dL. Furthermore, no dose level has been associated with exposure-related concerning safety signals, and a maximum tolerated dose (MTD) has not been defined. Treatment-related AEs were mostly grade 1/grade 2 gastrointestinal events. Given the predicted improved efficacy of higher doses, and lack of dose-limiting safety concerns, this study will investigate the potential for a greater benefit/risk for higher doses in patients with SCD.

In this study, baseline response will be characterized in participants receiving a 3-week treatment regimen with voxelotor 1500 mg and compared, within and across participants, to the response with the highest dose level tolerated at steady state. Dose escalation will be done in 3-week increments to assess tolerability at the escalated dose.

Figure 1: Relationships Between Change from Baseline in Hemoglobin at Week 24 and Percent Hemoglobin Occupancy

pkpd-wk24-hgb-20190508.pdf

C_{min} , minimum plasma concentration at steady state; CFB, change from baseline; Hb, hemoglobin.

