4.1. Inclusion Criteria

Participants who meet all the following criteria will be eligible for enrollment in the study:

1. Male or female with SCD
2. Documentation of SCD genotype HbSS or HbSB⁰
3. Age 18 to < 60 years, inclusive
4. Hemoglobin ≥ 5.5 and ≤ 10.5 g/dL during Screening, and considered stable and close to Baseline by the Investigator
5. For participants taking HU, the dose in mg/kg must be stable for at least 90 days prior to signing the informed consent form (ICF) and with no anticipated need for dose adjustments during the study, in the opinion of the Investigator.
6. Participants, who if female and of child-bearing potential, agree to use highly effective methods of contraception or practicing abstinence from study start to 30 days after the last dose of study drug, and who if male, agree to use barrier methods of contraception or practice abstinence from study start to 30 days after the last dose of study drug
7. Participant has provided documented informed consent

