10.4. Data Analysis

Data will be presented by maximum dose level.

A TEAE, defined as an event that occurs on or after Day 1 of study drug or the worsening of a pre-existing condition on or after Day 1 of study drug, will be classified according to the Medical Dictionary for Regulatory Activities (MedDRA). The incidence of TEAEs and relatedness to study drug, as assessed by the Investigator, will be summarized descriptively by maximum dose level tolerated.

Clinical laboratory tests, ECGs, and vital signs over time will be summarized by maximum dose level tolerated using descriptive statistics. Change from baseline in ECG intervals will be evaluated using descriptive statistics. If an effect on mean change from baseline in QTc interval exceeding 10 msec is observed, concentration-QTc analysis may be explored. Results from the diagnostic interpretation will be summarized by maximum dose tolerated.

An Hb responder endpoint, defined as an increase in Hb of > 1 g/dL compared to Baseline, will be summarized. Additionally, change from baseline in hemoglobin and clinical measures of hemolysis (unconjugated bilirubin, % reticulocyte, absolute reticulocyte, and LDH) will be summarized by maximum dose level tolerated using descriptive statistics.

The incidence of VOCs will be summarized by maximum dose tolerated.

The CGI-C and PGI-C will be summarized by maximum dose level tolerated.

Population PK analysis using nonlinear mixed-effect modeling will be performed to characterize voxelotor PK in plasma, and whole blood.

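### Section 1.5.1 announces a within-participant comparison with 1500 mg, but Section 10.4 plans only change and response against an undefined Baseline, with no paired contrast to the end of Period 1

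*Combined protocol and SAP*

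**What the plan says.** Section 1.5.1 (Study Rationale) says the study will assess doses above 1500 mg "and to compare these results to the 1500 mg dose". It then gives the method: "baseline response will be characterized in participants receiving a 3-week treatment regimen with voxelotor 1500 mg and compared, within and across participants". The other side of that comparison is each participant's top tolerated dose, once steady state is reached. For the top dose, assuming linearity, "the mean Hb occupancy is projected to be 49.3% with a Hb increase of 2.04 g/dL".

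The analysis sections are narrower. Section 10.1.2 defines the secondary Hb and hemolysis endpoints as change from Baseline and the proportion with an Hb rise above 1 g/dL over Baseline. Section 10.4 presents data by maximum dose level and says "An Hb responder endpoint, defined as an increase in Hb of > 1 g/dL compared to Baseline, will be summarized". It summarizes change from baseline in Hb and hemolysis measures by maximum dose tolerated, and laboratory tests over time in the same groups. The synopsis agrees. None of these names a difference from the end of Period 1, or a visit for the Hb endpoints.

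Baseline is not defined for Hb. Inclusion criterion 4 uses the word for the participant's usual level ("considered stable and close to Baseline by the Investigator"), while Section 1.5.1 applies it to the response on 1500 mg.

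**The concern.** Every participant takes 1500 mg for three weeks before any higher dose, and Section 1.4 reports a "dose-dependent increase in Hb within 2 weeks that is maintained through 24 weeks". So a change from a pre-treatment Baseline, measured at a higher dose, is the 1500 mg effect plus whatever the higher dose adds. The planned change and responder summaries do not separate the two.

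If doses above 1500 mg added nothing, the higher-dose groups could still show roughly the known 1500 mg result. In the Phase 3 study that was a mean rise of 1.1 g/dL and a responder rate of "51.1% for the voxelotor 1500 mg group". A reader could set the new results against those figures, but that is a comparison across studies. The rationale announced one within participants, and the design supplies the data for it.

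**Working it through.** **1. Figures taken as stated.** The sample size (up to 40, at least 6 at the study-level MTD; Section 10.2) has no formula behind it, and the regression coefficients for the 2.04 g/dL projection are not given. Neither can be reproduced, and neither is in dispute.

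**2. Share of the projected effect already present at 1500 mg** (Section 1.5.1; Week 24 means and a linear projection, so an illustration only).
- Increment: 2.04 − 1.10 = 0.94 g/dL.
- Shares: 1.10/2.04 = 54% and 0.94/2.04 = 46%.
- With the 1.14 g/dL of Section 1.4, the increment is 2.04 − 1.14 = 0.90 g/dL.

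**3. Responders if higher doses add nothing** (Phase 3 rate of 51.1%, also a Week 24 figure).
- 40 × 0.511 = 20.4 expected responders.
- 6 × 0.511 = 3.1 expected responders.

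**4. What the visit summaries over time provide.** Within a maximum-dose group with complete data, the same people contribute to both visits. Then mean(later) − mean(Period 2 Day 1) = mean(later − Period 2 Day 1). The mean paired difference is recoverable exactly. With missing values the two means come from different sets of people and the equality fails.

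**5. What they do not provide.** If both visits have SD s and within-person correlation r, the paired SD is s√(2(1 − r)). The documents do not give r, so a range is assumed:
- r = 0.3: 1.18s
- r = 0.5: 1.00s
- r = 0.7: 0.77s
- r = 0.9: 0.45s

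The range is 1.18/0.45 = 2.6-fold, so an interval cannot be recovered from visit means and SDs. Nor can each participant's responder status at both doses.

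**6. Precision of the paired mean.** The 95% half-width, in paired SDs, is t(0.975, n − 1)/√n:
- n = 6: 2.571/2.449 = 1.05
- n = 20: 2.093/4.472 = 0.47
- n = 40: 2.023/6.325 = 0.32

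n = 40 is a ceiling. It needs all 40 to be above 1500 mg with both values.

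**7. Elapsed time from Period 2 Day 1 to observation Week 12** (three-week periods, ignoring the ±3 days).
- All four periods completed: 9 + 12 = 21 weeks.
- Stopped in Period 3 and reduced to 2000 mg: 3 to 6, plus 12 = 15 to 18 weeks.
- Stopped in Period 4 and reduced to 2000 mg: 6 to 9, plus 12 = 18 to 21 weeks. Section 3.2 does not limit a reduction to one step.

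The same final dose can therefore go with different durations, and no fixed interval per dose is safe.

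**8. Data availability.** Hematology and chemistry are drawn on Day 1 of every period (Appendix A) and at observation visits from Day 7 to Day 168 (Appendix B). Footnote k of Appendix A, attached to CGI-C and PGI-C, treats Day 1 of Period 2 as Day 21 of Period 1.

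**The case against.** The comparison with 1500 mg appears only in the rationale. The secondary objective in Section 2.2 is to evaluate change in Hb and hemolysis, with no 1500 mg comparator, and Section 10 matches that objective. Section 10.2 calls the study exploratory and descriptive. The summaries over time already yield the mean difference when data are complete. A paired contrast would still not separate dose from time, because the order is fixed and there is no control.

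Most of this stands and limits the weight of the point. It does not remove it. Section 10.2 includes efficacy above 1500 mg in what the study is to describe, and following Section 10.4 as written does not deliver the comparison that the rationale sets out. The exploratory PK-PD objective does not fill the gap either, since Section 10.4 specifies only a population PK model and no Hb contrast.

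It could also be argued that Baseline means the end of Period 1, in which case change from Baseline would itself be the missing contrast. Nothing in the documents says so, and pre-treatment is the natural reading. The ambiguity is a further reason to define the term.

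A reader might infer that the plan shows no 1500 mg data at all, or cannot yield even a mean change from 1500 mg. The documents do not support that: the summaries over time include the period visits.

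**Conclusion.** The point holds as a mismatch between the stated comparison and the planned analysis. On the protocol's own projection, about 54% of the Hb change expected at 3000 mg would be the 1500 mg effect, and the planned change and responder summaries would not isolate the remaining 0.94 g/dL. What is missing is the paired spread, an interval, and responder status at both doses. This assumes a pre-treatment Baseline, Week 24 Phase 3 means, and the protocol's linear projection.

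The consequence is confined to how the secondary Hb and hemolysis results are read. A reader might go further and infer that the primary safety endpoint, the sample size or a hypothesis test is compromised. The documents do not support this: the primary endpoints are TEAEs and SAEs, the sample size rests on experience rather than on this contrast, and no test is planned. A reader might also expect the paired contrast to measure a pure dose effect, which this design cannot do. The change should be made, but the study does not fail without it.

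**What to change.** In Section 10.4, with the synopsis aligned:

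1. Define Baseline for Hb and hemolysis measures as the last value before the first Period 1 dose.
2. Add a descriptive within-participant difference in Hb, percent and absolute reticulocytes, unconjugated bilirubin and LDH. Take it from Period 2 Day 1 (end of 1500 mg) to one visit named in advance, for example observation Week 12 with Week 24 as supportive. Give 95% CIs by dose and pooled over participants whose observation-period dose is above 1500 mg. Leave participants returned to 1500 mg out of the pooled estimate and show them separately.
3. Cross-tabulate responder status against Baseline at the same two visits.
4. Report how many participants who started a dose above 1500 mg lack the later value, and why. Add a supportive summary using the last on-treatment value above 1500 mg. Flag values after a dose change or an RBC transfusion and repeat the summary without them. Both can occur on study: Section 3.2 allows dose modification during observation, and Section 5.8.3 requires discontinuation only for chronic transfusion.
5. State that the contrast is descriptive, confounded with time, based on participants who stayed on treatment, and imprecise in small dose groups. Report each participant's actual time since Period 2 Day 1 rather than a fixed range per dose.

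This covers Hb and hemolysis only. Section 1.5.1 also speaks of comparing tolerability, safety and PD, which this change does not address.

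The cost is analysis wording and a little more analysis work, with no added visits or samples. The headline for the higher doses may be less favourable.

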11. DIRECT ACCESS TO SOURCE DATA/DOCUMENTS

11.1. Source Data

Original documents, data, records (eg, clinic records, laboratory notes, memoranda, participant diaries or evaluation checklists, pharmacy dispensing records, recorded data from automated instruments, copies or transcriptions certified after verification as being accurate and complete, microfiches, photographic negatives, microfilm or magnetic media, X-rays, participant files, and records kept at the pharmacy, at the laboratories, and at medicotechnical departments involved in the clinical study), and all relevant sections of the participant's medical records and all other data collection made specific to this study constitute source documents.

The completed CRF is not a source document. The Investigator/institution will permit study-related monitoring, audits, IEC/IRB review and regulatory inspection by providing direct access to source documents.

11.2. Data Collection

The Investigator will be responsible for maintaining accurate and adequate case records (source documents) from which data will be transcribed to CRFs designed to record data pertinent to this study. All relevant observations and data related to the study will be recorded. This will include medical and medication history, physical examinations, a checklist of inclusion and exclusion criteria, investigational treatment administration, a record of sample collection, clinical assessments, AEs, and final evaluation(s). The monitor will review all CRFs and compare data to that contained in clinic notes and participants' source documents/medical records.

Data for each participant will be recorded on the CRF unless transmitted to the sponsor or designee electronically, eg, laboratory data. A CRF must be completed for every participant enrolled in the study. When data are complete, the Investigator or medically qualified Sub-Investigator listed on Form FDA 1572 will apply his/her signature on the CRF indicating he/she has reviewed and approves of the data collected on the CRF.

11.3. Essential Documentation Requirements

The Sponsor or Sponsor's representative will collect from the investigational site the required essential regulatory documents per International Council for Harmonisation (ICH) guidance prior to voxelotor shipment to the site.

12. QUALITY CONTROL AND QUALITY ASSURANCE

12.1. Monitoring

Site personnel will be provided with training on how to collect quality data for the study, and a Sponsor monitor will be contacting the site periodically to review study conduct and data recorded at the site. At the Sponsor's discretion, on-site monitoring visits may be conducted prestudy, during the study, and following study completion. These visits are to provide the Sponsor with the opportunity to evaluate study progress; verify the accuracy and completeness of source data and CRFs; and ensure that all protocol and Good Clinical Practice (GCP) requirements, applicable US FDA or country-specific regulations, and Investigator obligations are being fulfilled. The Sponsor may terminate study participation by a clinical study site if study-site personnel do not follow the protocol or GCPs. Additionally, individual participants may be excluded if a medical records review indicates protocol violations or if other factors appear to jeopardize the validity of the study.

The Investigator agrees to cooperate with the monitor to ensure that any problems detected during the course of these monitoring visits are resolved.

12.2. Quality Control and Quality Assurance

GBT may conduct a quality assurance audit(s) of this study. If such an audit occurs, the Investigator agrees to allow the auditor direct access to all relevant documents (eg, all participant records, medical records and CRFs) and access to all corresponding portions of the office, clinic, laboratory, or pharmacy which may have been involved with the study. The Investigator will allocate his or her time and that of the study-site personnel to the auditor to discuss findings and any relevant issues. In addition, regulatory agencies may conduct a regulatory inspection of this study. If such an inspection occurs, the Investigator agrees to notify GBT upon notification by the regulatory agency. The Investigator agrees to allow the inspector direct access to all relevant documents and to allocate his or her time and that of the study-site personnel to the inspector to discuss findings and any relevant issues. The Investigator will allow GBT personnel to be present as an observer during a regulatory inspection, if requested.

12.3. Laboratory Accreditation

The laboratory facility used for analysis of clinical laboratory samples must provide evidence of adequate licensure or accreditation. Copies of laboratory certification, licensure, and reference ranges (as appropriate) will be supplied to the Sponsor prior to study initiation. The Sponsor or designee should be notified of any changes in reference range values or certification/license renewal during the course of the study.

13. REGULATORY, ETHICAL AND LEGAL OBLIGATIONS

13.1. Ethical Conduct of the Study

The Investigator will ensure that this study is conducted in full conformity with the current revision of the 1964 Declaration of Helsinki.

The Investigator is generally not to deviate from the protocol. In medical emergencies, the Investigator will use medical judgment and will remove the participant from immediate hazard. The Investigator will immediately notify the Sponsor and IEC/IRB regarding the nature of the emergency and the course of action taken. The Investigator is to notify the Sponsor of any inadvertent protocol deviations upon discovery and is to document the deviations appropriately in the study files or on the CRFs. The Sponsor assumes no responsibility or liability for any unapproved deviations. Major changes in the protocol initiated by the Sponsor will be provided as an amendment and will be approved by the IEC/IRB prior to implementation (refer to Section 13.4).

13.2. Good Clinical Practice

The study will be conducted according to the protocol; guidelines established by ICH for GCP in clinical studies; US regulations (21 CFR Parts 50, 54, 56, and 312); and country-specific requirements, as applicable.

13.3. Written Informed Consent

Each individual will be provided with oral and written information describing the nature, purpose and duration of the study, participation/termination conditions, and risks and benefits. Prior to initiation of any study-related procedures, participants will sign and date the ICF to participate in the study. In the event of a pregnancy in the female partner of a male participant, a pregnancy consent form will be provided to allow the follow-up of the pregnancy.

13.4. Independent Ethics Committee, Institutional Review Board, and Regulatory Approval

The Investigator must inform, and obtain approval from, the IEC/IRB for the conduct of the study at named sites, for the protocol, the Participant ICF, and any other written information that will be provided to the participants and any advertisements that will be used. Written approval must be obtained prior to recruitment of participants into the study and shipment of investigational agent.

Proposed amendments to the protocol and documents must be discussed with the Sponsor and CRO, and then submitted to the IEC/IRB for approval as well as submitted to regulatory authorities for approval prior to implementation. Amendments may be implemented only after a copy of local IEC approval letter has been transmitted to the Sponsor. Amendments that are intended to eliminate an apparent immediate hazard to participants may be implemented prior to receiving Sponsor or IEC/IRB approval. However, in this case, approval must be obtained as soon as possible after implementation.

The Investigator will be responsible for ensuring that an annual update is sent to the EC to facilitate their continuing review of the study (if needed) and that the IEC/IRB is informed about the end of the study. Copies of the update, subsequent approvals, and final letter must be sent to the Sponsor. The Investigator will inform the IEC/IRB of any reportable AEs.

